#### *4.3.8.7 Physical Examination*

The overall clinical assessment of the physical examination is recorded for clinical significance. Results of physical examination will be summarized by shift tables from baseline by scheduled time of evaluation, including the last post-baseline and the maximum post-baseline value. Both scheduled and unscheduled post-treatment values will be considered for summaries of the last and maximum post-baseline values.

The following categories will be used, from worst to best-case: Abnormal clinically significant , Abnormal not clinically significant, Normal.

Physical examination will be analyzed only for the EOT analysis.

#### *4.3.8.8 Anti-Drug Antibodies (ADA)*

A listing of subjects with any positive ADA ordered chronologically will be presented. The listing will include the day on which the ADA were positive, and if positive the titer.

#### 4.3.9 Secondary Endpoints

This SAP will follow the estimand framework outlined in the ICH-E9(R1) addendum (FDA 2019) for the definition of the analysis of key secondary efficacy endpoint: Overall response on the lower GI according to MAGIC assessment.

Missing data:

- The general approach is that subjects with missing data or invalid such that the response cannot be determined will be included in the analysis as non-responders.
- Lost on follow-up: subject included but response data are missing and will be imputed as non-responder until the clinical cut-off date.
- Trial discontinuation: subject included but response data are missing and will be imputed as non-responder until the clinical cut-off date.

Censored data:

- At the time of the analysis, subject visits not yet completed and with expected date beyond the clinical cut-off date will be indicated as censored (e.g. a subject visit expected 7 days after the clinical cut-off date will be censored; for subjects deceased prior the clinical cut-off date, visits that would have occurred after the clinical cut-off date will be censored).
- If the subject scheduled visit is not expected to be completed, the visit is censored (e.g. scheduled subject visit week 12 prior the clinical cut-off but excluded for the subject who did not enter treatment extension period due to complete responder status at week 8; scheduled visit at week 11 for a subject who did not enter treatment extension period due to death at week 5).
- For all enrolled subjects, all visits covering the initial treatment phase (week 1 to 8 included) and all follow-up visits are expected to be completed.
- A censored subject visit does not contribute to the denominator of the visit.
- Across all scheduled visits, the denominator plus the number of censored subjects is constant and equal to the number of subjects in the analysis set (and treatment group when applicable).

##### 4.3.9.1 MAGIC Assessment

The Overall Clinical Grade and the MAGIC organ staging assessment (skin, lower GI, upper GI, liver) will be tabulated by apaglutide dose group (Low Dose, High Dose, Total Randomized, Low Body Weight, Total) at screening, baseline, Day 14, Day 28, Day 56, Day 91, Day 119, Day 147, and Day 182 visits.

#### 4.3.9.2 Overall/Lower GI Response Based on MAGIC Score by Time Point

The Lower GI MAGIC score response and the total MAGIC score response will be calculated per the definition described in Appendix A based on the Lower GI MAGIC score and the total MAGIC score, respectively, at a given time point, compared to the corresponding score at Baseline. It follows that every observed Lower GI MAGIC Stage response at a time point will be classified as *Progression, Stable Disease, Partial Response, and Complete Response*. Similarly, every observed Total MAGIC score response will be classified into the same categories augmented by the Mixed Response category. Subjects with missing MAGIC assessments after the first dose of apraglutide will be included as non-responders for response rate calculation. Censored assessments will not be included in the response rate calculation. Note: if a subject initiated an additional, new systemic therapy for an earlier progression, mixed response, or non-response of aGVHD, both the lower GI-aGVHD response and the overall response at subsequent time points will be assigned as non-responders until the clinical cut-off date. Additional new systemic therapies are only those that started after the first dose of apraglutide and are captured in the CM and PR eCRF forms.

#### **Overall Response Rate at Day 56 on the Lower GI MAGIC Score**

The key secondary objective listed in protocol is to evaluate the overall response rate (partial response [PR] and complete response [CR]) at Day 56 on the Lower GI MAGIC score in subjects with SR lower GI-aGVHD Grade II to IV MAGIC that are treated with apraglutide, SS, and RUX.

To assess the key secondary objective, the key secondary efficacy estimand is defined by the following key attributes, according to the framework provided in ICH E9(R1) (FDA 2021):

- **Treatment:** weekly subcutaneous administration of low, or high, or low body weight dose of apraglutide on top of ruxolitinib within 72 hours prior the first administration of apraglutide excluding the use of additional systemic therapy from first administration of apraglutide.
- **Population:** Subjects with SR lower GI-aGVHD.
- **Population-level summary:** the proportion of subjects achieving overall response (CR+PR) on the Lower GI MAGIC score.
- **Variable:** Overall response on the Lower GI MAGIC Score.
- **Analysis Model:** use of FAS subjects for calculation of the proportion of overall response (CR and PR) on the Lower GI MAGIC score at Day 56 with a two-sided 95% confidence interval using Clopper-Pearson exact method.
- **Intercurrent events and strategy:**

- Terminal events:
  - ICE1: as death precludes further observations, based on composite strategy, assumes non-response from death event until the Primary Analysis clinical cut-off date included.
- Treatment change:
  - ICE2: in the event of treatment discontinuation, following treatment policy strategy; if a subject withdraws from treatment, observed values will be used regardless of the ICE.
  - ICE3: in the event of pausing or dose reduction of apaglutide, following treatment policy strategy, observed values will be used regardless of the ICE.
- Additional / alternative treatment:
  - ICE4: when additional systemic therapies are used for any earlier progression, mixed response or stable aGVHD, following hypothetical strategy, observed data will be discarded, and from the point of ICE, subjects will be considered as non-responder, as if treatment failure, until the Primary Analysis clinical cut-off date included.
  - ICE5: when a subject receives Donor Lymphocyte Infusions or Stem cell boost as concomitant medication or procedures, as per “treatment policy” strategy, all observed values will be used regardless of the ICE.
  - ICE6: Budesonide use or other non-absorbable steroids given orally: following treatment policy, observed values will be used regardless of the ICE.
  - ICE10 (additional from interim analysis): interruption of 14 or more days of RUX, as per “treatment policy” strategy, all observed values will be used regardless of the ICE.
- Other:
  - ICE7: Underlying hematological disease progression or relapse, following treatment policy, all observed values will be used regardless of the ICE.
  - ICE8: Development of cGVHD, following treatment policy, all observed values will be used regardless of the ICE.
  - ICE9: CTR-reportable protocol deviation that significantly affects subject safety or efficacy (as defined in the Protocol Deviation Plan), all observed values will be used regardless of the ICE.

The number and percentage of subjects with overall response (PR and CR) at Day 56 on the Lower GI MAGIC score along with the two-sided 95% confidence intervals using Clopper-Pearson exact method will be provided by apraglutide dose levels and in total. In addition, the number and percentage of subjects with CR and the number and percentage of subjects with PR at Day 56 on the Lower GI MAGIC score will also be summarized, respectively.

**Analysis of Overall Response Rate on Lower GI MAGIC Score at Day 14, Day 28, Day 91, Day 119, Day 147, Day 182.**

The description of the estimand is similar to the one described for the analysis of the “Overall Response Rate at Day 56 on the Lower GI MAGIC Score” with as a variation:

- **Analysis Model:** use of FAS subjects for the calculation of the proportion of overall response (CR and PR) on the Lower GI MAGIC score at time points Day 14, Day 28, Day 91, Day 119, Day 147, Day 182 relative to Baseline. The number and percentage of subjects with CR and the number and percentage of subjects with PR on the Lower GI MAGIC Score at a given time point will also be summarized.

The overall response rate on the lower GI MAGIC Score will be presented graphically over time.

**Analysis of Overall Response Rate on Total MAGIC Score Day 14, Day 28, Day 56, Day 91, Day 119 ,Day 147, Day 182.**

The analysis described in the section “Overall Response Rate at Day 56 on the Lower GI MAGIC Score” will be conducted similarly for the Overall Response Rate on Total MAGIC Score for the following time points if available at the time of the Primary analysis: Day 14, Day 28, Day 56, Day 91, Day 119, Day 147 and Day 182 on the total MAGIC Score.

The present estimand description differs from the “Overall Response Rate at Day 56 on the Lower GI MAGIC Score”:

- **Population-level summary:** the proportion of subjects achieving overall response (CR and PR) on the total MAGIC score.
- **Variable:** overall response on the total MAGIC Score
- **Analysis Model:** use of FAS subjects for the calculation of the proportion of overall response (CR and PR) on the total MAGIC score at Day 14, Day 28, Day 56, Day 91, Day

**119, Day 147 and Day 182** along with the corresponding two sided 95% confidence intervals using Clopper-Pearson exact method.

The overall response rate on the total GI MAGIC Score will be displayed graphically over time.

**Sensitivity Analysis for Overall Response Rate at Day 56 on the Lower GI MAGIC Score and on the Total MAGIC Score**

To evaluate the robustness of the analysis of the Day 56 secondary endpoint sensitivity analyses evaluating alternative response definitions taking account for the potential influence of intercurrent will be made. Starting from the estimand describing the analysis "Overall Response Rate at Day 56 on the Lower GI MAGIC Score", the sensitivity analysis will consider simultaneously alternative ICE strategies:

- ICE2 alternative: in the event of treatment discontinuation, following composites strategy, subjects will be considered as non-responder from the point of the ICE as if treatment failure, until the analysis clinical cut-off date included, censored beyond.
- ICE3 alternative: in the event of pausing or dose reduction of apaglutide, following composites strategy, subjects will be considered as non-responder from the point of the ICE as if treatment failure, until the analysis clinical cut-off date included, censored beyond.
- ICE6 alternative: Budesonide use or other non-absorbable steroids given orally, following composites strategy, subjects will be considered as non-responder from the point of the ICE as if treatment failure, until the analysis clinical cut-off date included, censored beyond.
- ICE10 alternative: Rux interruption, following composites strategy, subjects will be considered as non-responder, as if treatment failure from the point of the ICE until the analysis clinical cut-off date included, censored beyond.
- ICE5 alternative: Donor Lymphocyte Infusions or Stem cell boost as concomitant medication, following composites strategy, subjects will be considered as non-responder, as if treatment failure from the point of the ICE, until the analysis clinical cut-off date included, censored beyond.

*4.3.9.3 Durable overall response on the Lower GI MAGIC Score from Day 28 to Day 56*

Durable overall response rate on the Lower GI MAGIC Score from Day 28 to Day 56 is defined as the proportion of subjects who had a response (either CR responder or PR responder) on the lower GI at Day 28 and remain a CR responder or PR responder on the lower GI at Day 56.

The ICE events and strategies defined in section 4.3.9.2 will be applied consistently for the estimation of CR and PR at Day 28 and Day 56 on which relies the durable overall response on the Lower GI MAGIC score.

The number and percentage of subjects with durable overall response on the Lower GI MAGIC score from Day 28 to Day 56 will be provided by apaglutide dose levels and in total along with the corresponding two-sided 95% confidence intervals using Clopper-Pearson exact method.

Percentage is computed using the number of subjects in treatment group as denominator.

Subjects with missing data such that the response cannot be determined at Day 56 (missing MAGIC score assessment at Day 56, or discontinued the trial prior to Day 56) will be handled as non-responders.

*4.3.9.4 Durable overall response on the Total MAGIC Score from Day 28 to Day 56*

Durable overall response rate from Day 28 to Day 56 on the Total MAGIC Score is defined as proportion of subjects who had a response (either CR responder or PR responder) on the total MAGIC score at Day 28 and remain a CR responder or PR responder on the total MAGIC score at Day 56.

Percentage is computed using the number of subjects in treatment group as denominator.

The analysis of the durable overall response rate from Day 28 to Day 56 on the Total MAGIC Score will be performed similarly to the analysis of durable overall response on the Lower GI MAGIC score described in Section 4.3.9.3.

*4.3.9.5 Durable overall response on the Lower GI MAGIC Score from Day 56 to Day 91*

Durable overall response rate on the Lower GI MAGIC Score from Day 56 to Day 91 is defined as the proportion of subjects who had a response (either CR responder or PR responder) on the lower GI at Day 56 and remain a CR responder or PR responder on the lower GI at Day 91.

Percentage is computed using the number of subjects in treatment group as denominator.

The ICE events and strategies defined in section 4.3.9.2. will be applied consistently for the estimation of CR and PR at Day 56 and Day 91 on which relies the durable overall response on the Lower GI MAGIC score.

The number and percentage of subjects with durable overall response on the Lower GI MAGIC score from Day 56 to Day 91 will be provided by apaglutide dose levels and in total along with

the corresponding two-sided 95% confidence intervals using Clopper-Pearson exact method. Percentage is computed using the number of subjects in treatment group as denominator. Subjects with missing data such that the response cannot be determined at Day 91 (missing MAGIC score assessment at Day 91 or discontinued the trial prior to Day 91) will be handled as non-responders.

*4.3.9.6 Durable overall response on the Total MAGIC Score from Day 56 to Day 91*

Durable overall response rate from Day 56 to Day 91 on the Total MAGIC Score is defined as proportion of subjects who had a response (either CR responder or PR responder) on the total MAGIC score at Day 56 and remain a CR responder or PR responder on the total MAGIC score at Day 91.

Percentage is computed using the number of subjects in treatment group as denominator.

The analysis of the durable overall response rate from Day 56 to Day 91 on the Total MAGIC Score will be performed similarly to the analysis of durable overall response on the Lower GI MAGIC score described in Section 4.3.9.5.

*4.3.9.7 Individual duration of lower GI response*

Duration of lower GI response is defined as the duration from the first date a subject is identified as a Lower GI MAGIC Score CR or PR responder until the next date a subject is Lower GI MAGIC Score SD/PD (i.e., return to baseline or worsening), or dead, whichever occurs first.

This is only defined for subjects with partial response or complete response. The best response is derived from assessments performed from the start of the treatment up to Day 91 or the start of additional systemic therapy for GI-aGVHD, whichever occurs first.

Subject for which neither “return to baseline or worsening” or “dead” event occurs will be right censored at their last MAGIC assessment visit. The ICE events and strategies defined in section 4.3.9.2. will be applied consistently for the estimation of CR and PR.

The event or censoring date will be determined based on the conventions listed in Table 4-3.

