Subjects with missing data such that the Day 56 lower GI response cannot be determined will be included in the preceding analysis as non-responders consistent with intent to treat philosophy. A sensitivity analysis will also be performed based only on those subjects with non-missing data being consistent with a missing at random assumption.

To evaluate the robustness of the analysis of the Day 56 secondary endpoint, sensitivity analyses evaluating alternative response definitions taking account for the potential influence of intercurrent events like increase in steroids, development of infectious colitis, relapse, and the use of budesonide or other non-absorbable steroids will be made. Details of these analyses will be outlined in the SAP.

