## 6 CHANGES FROM PROTOCOL-SPECIFIED STATISTICAL ANALYSES

1. Analysis Day will not include Day 0, per CDISC compliance, whereas protocol considers Day 0. The distinction between visits and analysis days is detailed in Section 4.1.1.
2. Treatment description is broken down into main treatment (W0-W7) and extension treatment (W8-W13), for analysis purpose.
3. Sample size determination explicitly refers to durable overall response on the Lower GI MAGIC score.
4. Wording of the definition of Additional systemic therapies in Appendix A has been added for completeness.
5. The AE Grading for on-sites reactions was contradictory in the protocol and is clarified in Section 4.3.8.1
6. The SAS1 and SAS2 analysis population were merged in a single analysis population, as the analysis output formatting can provide equivalent information.
7. Due to the absence of adequate historical control, the comparison to external data on BAT was not planned for the Primary Analysis.
8. Brookmeyer-Crowley confidence interval levels are set to 95% (instead of 90% in protocol) for consistency of levels between confidence intervals.
9. Duration of response from Day 28 and Day 56 on the total MAGIC score are analyzed regardless of follow-up duration, with right-censoring for subjects who did not reach the 182 days of follow-up at data cut-off.

10. The incidence of infections and sepsis from baseline are analyzed up to Day 91 but also up to the end of the trial.
11. Physical examination was added in the list of safety endpoints as the protocol states that physical examination will be analyzed as safety endpoint.
12. The following endpoint listed in the protocol was removed from the list of endpoints as no formal comparison will be performed: Effect of the two dose groups on safety/tolerability and efficacy

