
“Additional systemic therapy” definition for the complete and partial response definition
	
Any GVHD systemic therapy being started after apaglutide initiation to achieve GVHD control, i.e. any medication or procedure marked as Reason for medication = “aGVHD treatment” and “Is this an additional, new systemic therapy for an earlier progression, mixed response or non-response of aGVHD?” = Yes in the CM or PR page of the eCRF.
 
Note:
 
 
- Increases or addition of a new systemic steroid will not be counted as new or additional GVHD therapy.
 
Budesonide and beclametasone not to be considered as new GVHD therapy
 
- Change in dose of CNIs will not be considered as additional GVHD therapy if already given prior to apaglutide
 
 
New CNIs after apaglutide initiation should be considered as a new systemic therapy, if marked as “aGVHD treatment” and “Is this an additional, new systemic therapy for an earlier progression, mixed response or non-response of aGVHD?”; these will not be considered as new therapy if marked as “prophylaxis for a drug side effect”.

Complete lower gastrointestinal (GI)-aGVHD response
	
The resolution of all lower GI-aGVHD signs and symptoms (score of 0 for aGVHD grading) of GVHD without administration of additional systemic therapies for any earlier progression, or non-response of lower GI-aGVHD.

Partial response
	
An improvement of one stage in one or more organs involved with aGVHD signs or symptoms without progression in other organs or sites without administration of additional systemic therapies for an earlier progression, mixed response, or non-response of aGVHD

Partial lower GI-aGVHD response
	
An improvement of one stage in the signs and symptoms of lower GI-aGVHD without administration of additional systemic therapies for any earlier progression or non-response of lower GI-aGVHD.

Lack of response	Defined as stable disease, mixed response, or progression
Stable disease	An absence of improvement in all organs involved by aGVHD, without worsening in all involved organs or development of signs or symptoms of aGVHD in a new organ
Stable disease (lower GI-aGVHD)	An absence of improvement or absence of worsening in lower GI-aGVHD
Mixed response	An improvement of at least 1 stage in the severity of aGVHD in one organ accompanied by progression in another organ or development of signs or symptoms of aGVHD in a new organ

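### The SAP's Day 56 sensitivity analysis leaves out systemic steroid increase, an example the protocol gives for it, and SAP Section 6 does not declare or justify this

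*SAP*

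**What the plan says.** **Protocol 7.8.1** says that sensitivity analyses of the Day 56 endpoint will be made with alternative response definitions, to allow for "intercurrent events like increase in steroids, development of infectious colitis, relapse, and the use of budesonide or other non-absorbable steroids". It leaves the details to the SAP. Non-absorbable steroids are listed separately, so the first example is most naturally read as systemic steroid.

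**SAP 4.3.9.2, sensitivity analysis**, carries the sentence over without the examples: "sensitivity analyses evaluating alternative response definitions taking account for the potential influence of intercurrent will be made". It then switches five events to a composite strategy, all at once: ICE2 (treatment discontinuation), ICE3 (apraglutide pause or dose reduction), ICE5 (donor lymphocytes or stem cell boost), ICE6 and ICE10 (RUX interruption). The only steroid item is "ICE6 alternative: Budesonide use or other non-absorbable steroids given orally, following composites strategy, subjects will be considered as non-responder".

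**SAP 4.3.9.2, main estimand**, defines ICE1 to ICE10. None is a systemic steroid increase. The nearest is "ICE4: when additional systemic therapies are used for any earlier progression, mixed response or stable aGVHD, following hypothetical strategy, observed data will be discarded", after which the subject is a non-responder. **Appendix A** closes that route: "Increases or addition of a new systemic steroid will not be counted as new or additional GVHD therapy".

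**SAP Section 6** lists 12 changes from the protocol. The closest is item 4: "Wording of the definition of Additional systemic therapies in Appendix A has been added for completeness". It does not mention the sensitivity analysis.

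**The concern.** Both randomized arms receive apraglutide, and SAP Section 6 item 7 adds: "Due to the absence of adequate historical control, the comparison to external data on BAT was not planned for the Primary Analysis". The Day 56 rate therefore stands largely alone in the Primary Analysis, and its credibility rests on how it holds up against rival explanations. More systemic steroid is one of these; newly started RUX is another.

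Steroid change during treatment is foreseeable. Protocol 4.2.2.2 lets the investigator change the systemic steroid dose. Protocol 2.2.2 makes SS/RUX adjustment the first recommended step if GI symptoms worsen shortly after apraglutide starts. It gives no direction, but an increase is an obvious possibility.

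As written, no planned Day 56 response analysis shows how much of the rate comes from subjects whose systemic steroid was increased. A reader could take agreement between the main and sensitivity rates as reassurance on a point the sensitivity analysis never tests.

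**Working it through.** The plan gives no figure for this point, so the check is mainly textual.

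**1. Coverage of the protocol's four examples**

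| Example in protocol 7.8.1 | Main estimand (SAP 4.3.9.2) | Sensitivity alternative |
|---|---|---|
| Increase in steroids | Not an ICE; kept out of ICE4 by Appendix A | None |
| Infectious colitis | Not an ICE | None |
| Relapse | ICE7, treatment policy | None |
| Budesonide or other non-absorbable steroids | ICE6, treatment policy | Composite, non-responder |

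One of four has an alternative. The SAP varies 5 of its 10 ICEs. Section 6 items declaring the difference: 0 of 12.

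**2. Two subjects traced through the rules.** Both improve by one lower GI stage at Day 56 and have no other event leading to non-response.

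- Subject A has a systemic steroid increase and no new agent. ICE4 does not apply because of Appendix A, and no alternative applies. Responder in the main analysis, responder in the sensitivity analysis.
- Subject B is given oral budesonide. Responder in the main analysis (ICE6, treatment policy), non-responder in the sensitivity analysis (ICE6 alternative).

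The SAP gives no reason for the difference.

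**3. Other uses of steroid dose in the SAP**

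- 4.3.6.2 summarizes weekly weight-normalized dose by dose group. It does not link dose to individual response.
- 4.3.9.9 counts an increase above 2 mg/kg/day methylprednisolone equivalent as an event for duration of response on the total MAGIC score. It applies only to subjects already counted as responders and does not re-test Day 56 lower GI response.

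**4. Scale.** Inputs: 30 randomized 1:1, so 15 per arm (protocol 7.4). Reclassifying one responder changes the rate by 1/n:

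- 1/15 = 6.7 points
- 1/30 = 3.3 points

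Illustration for the 30 randomized, assuming 20 responders (the documents give neither this number nor a count of steroid increases), with the SAP's 95% Clopper-Pearson intervals:

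| Responders reclassified | Rate | 95% CI |
|---|---|---|
| 0 | 20/30 = 66.7% | 47.2 to 82.7 |
| 1 | 19/30 = 63.3% | 43.9 to 80.1 |
| 2 | 18/30 = 60.0% | 40.6 to 77.3 |
| 3 | 17/30 = 56.7% | 37.4 to 74.5 |

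These shifts are small against the width of the intervals.

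**The case against.** The sponsor has a fair case.

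- **The list is illustrative.** Protocol 7.8.1 introduces the events with *like* and leaves the details to the SAP. Being named first carries no stated priority. A reader might infer that the SAP breaks a binding list; the documents do not support that. What stands is that the protocol says analyses of this kind will be made, and the SAP drops this example without comment.
- **Steroids are background therapy.** Adjustment is permitted, Appendix A excludes it openly, and counting protocol-conforming care as failure is debatable. This supports treatment policy in the main analysis, which is not disputed. It does not explain why budesonide is tested and systemic steroid is not.
- **Some increases are already caught.** If an increase is accompanied by a new systemic agent marked in the eCRF as additional aGVHD therapy, ICE4 applies. The gap is limited to increases without a new agent.
- **Disclosure can come later.** Protocol 7.9 requires deviations from the statistical plan to be reported with a rationale in the trial report. That helps, but a reason given before results are seen is worth more.
- **The analysis cannot settle attribution.** Every subject starts RUX with apraglutide or within 72 hours before it. This is true; the analysis would address one rival explanation only.

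A reader might also infer that relapse and infectious colitis are gaps of equal weight. They are secondary. Relapse has a stated strategy ("ICE7: Underlying hematological disease progression or relapse, following treatment policy, all observed values will be used regardless of the ICE"), and protocol 5.5 already asks the investigator to judge whether diarrhea is due to GVHD or to infection.

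**Conclusion.** The point holds. Systemic steroid increase is absent from the Day 56 sensitivity analysis, excluded from ICE4, and not declared in Section 6. A subject with an increase but no new agent and no other non-response event is a responder in both analyses.

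The effect could be zero or several responders, at 6.7 points each in an arm of 15 or 3.3 points each in 30. The illustration above rests on assumed counts. A reader might infer that the reported Day 56 rate is inflated; the documents do not show that, because they give no count of increases. The primary objective is safety, and no decision rule depends on the rate. This is a change that should be made because it is cheap and tests a rival explanation the protocol itself names. It is not a flaw that undermines the trial.

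**What to change.** Amend SAP 4.3.9.2 as follows.

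1. Add systemic steroid increase between first dose and the Day 56 assessment as an intercurrent event, with treatment policy in the main analysis.
2. Add a composite alternative (non-responder from the event) to the Day 56 sensitivity analysis, and also show it on its own, because the existing alternatives are applied together.
3. Define the event as an increase to more than 2 mg/kg/day methylprednisolone equivalent (the threshold in SAP 4.3.9.9) that is also above the dose at randomization (summarized in SAP 4.3.3). The second condition is needed because the steroid-refractory criteria in protocol 3.2.1 involve prior dosing at about that level, so some subjects may already be there at entry.
4. Derive it from the eCRF dose records required by protocol 4.2.3.2, with the baseline-weight normalization and gap imputation already in SAP 4.3.6.2. Where only a weekly total is available, the threshold corresponds to more than 7 × 2 = 14 mg/kg per week.
5. Optional: a descriptive count of Day 56 responders with any smaller re-escalation, limited to aGVHD where the reason-for-medication field cited in Appendix A allows. These should not count as failures, since minor taper reversals would be included.

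If the sponsor leaves the steroid analysis out on purpose, Section 6 should declare and justify it. Section 6 should also state that relapse and infectious colitis have no alternative strategy, and why. If the Primary Analysis has already been run, label the added analysis with the date it was specified.

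Cost: SAP wording and a little programming, no new data collection for the main flag, and a sensitivity rate that may be lower. The main estimand does not change.
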